#### STATISTICAL ANALYSIS PLAN:

**Missing Data:** Potential sampling biases will be identified by multiple logistic regression analyses examining whether key predictors at baseline (primary and secondary outcome measures; demographics) are associated with study retention. Should analyses reveal that dropout is differentially associated with outcomes, multiple imputation will be used.

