#### Criteria for exclusion:

None

**Sample size:** For aim 1 and 3, a Monte Carlo-based power estimate was derived using Mplus with 10,000 replications. For the sample size of 180, assuming a Type I error rate of 5%, a two-tailed test, statistical power was .83 to detect a medium-sized effect (r = .30) of randomization group on longitudinal changes, given an expectation of a small (r = .15) effect for the control group. For aim 2, power was calculated using G\*Power. Given the brevity of the three-month follow-up questionnaire, a 10% attrition rate was assumed. Assuming a Type I error rate of 5%,

a two-tailed test, and a 25% rate of seeking EBPs in the researcher-only condition, statistical power was .82 to detect a medium effect (odd ratio = 1.72).

**Randomization:** Participants will be cluster randomized by school using restricted randomization with Excel's random number generator.

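### Multiple imputation for three-month CBT seeking depends on a retention check that leaves out condition and post-presentation intention and often misses moderate dropout effects; it should be used in every case

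*Combined protocol and SAP*

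**What the plan says.** The SAP's Missing Data paragraph has two steps. Potential bias is looked for by "multiple logistic regression analyses examining whether key predictors at baseline" relate to retention, and the predictor list is "key predictors at baseline (primary and secondary outcome measures; demographics) are associated with study retention". Then comes the rule: "Should analyses reveal that dropout is differentially associated with outcomes, multiple imputation will be used". The paragraph gives no test or threshold for the rule, no imputation model, and no method for the case where the rule is not met.

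The Sample size paragraph states that "a 10% attrition rate was assumed" for the three-month questionnaire. Under Measures, three-month CBT seeking (yes/no) is the second primary outcome. Under Planned Analyses it is analysed by a binary logistic regression at that one time point, on condition and youth anxiety. The five pre/post outcomes are analysed by multilevel models with a random intercept.

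**The concern.** The method for a primary outcome is chosen by a preliminary test that is poorly matched to the question.

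- **Wrong variables.** Condition is not a listed predictor, so unequal dropout between arms is not examined. Post-presentation intention, probably the best available predictor of seeking, is not a baseline measure and is also left out. Youth anxiety, the covariate in the seeking model, is classed as exploratory and so falls outside the list as written.
- **Unobservable target.** Three-month seeking has no baseline value and is missing in exactly those who drop out. Its association with dropout cannot be tested from the data.
- **Little information.** About 18 dropouts carry little evidence about up to 19 listed variables.

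If the check misses, the logistic regression drops everyone without a three-month answer. Pre and post intention may be on file for many of those caregivers and would go unused. The pre/post multilevel models are much less exposed, because a likelihood fit uses all available observations. The issue is therefore sharpest for Hypothesis 1b.

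**Working it through.** **Inputs from the plan.** N = 180; 10% attrition; 25% seeking in the researcher-only arm; odds ratio 1.72. Number of dropouts: 180 × 0.10 = 18, leaving 162. Allocation is not stated; 1:1 is assumed, so 81 per arm.

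**Number of predictors.** Five baseline scales: intention, knowledge, subjective norms, attitudes, stigma. Demographics: age, gender, race, ethnicity and nativity for caregiver and youth (10), caregiver education, income and religion (3), and youth insurance (1), which makes 14. Total 19 before dummy coding. Dropouts per predictor: 18/5 = 3.6 with the scales alone, 18/19 = 0.9 with everything. Because the plan does not fix the number, 5, 12 and 19 are shown.

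**Power to detect one true predictor** (two-sided p < 0.05 assumed as the trigger). Power = Φ(√(N·p·(1−p))·ln OR − 1.96), with √(180 × 0.1 × 0.9) = 4.025.

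- OR 1.3 per SD: 4.025 × 0.262 − 1.96 = −0.90, power 18%.
- OR 1.5: 4.025 × 0.405 − 1.96 = −0.33, power 37%.
- OR 2.0: 4.025 × 0.693 − 1.96 = 0.83, power 80%.

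Simulation of the multi-predictor regression gives about 36% at OR 1.5 and about 75% at OR 2.0.

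**Chance that at least one predictor is significant** (simulated; independent standardized predictors, at most one of them real):

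| Predictors | No association | OR 1.5 per SD | OR 2.0 per SD |
|---|---|---|---|
| 5 | 22-24% | 48% | 80% |
| 12 | 49% | 63% | 85% |
| 19 | 64-68% | 77% | 91% |

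For comparison, 1 − 0.95^k gives 23%, 46% and 62% for k = 5, 12 and 19. Going from 5 to 19 predictors with no association raises the firing rate by more than 40 points. Going from no association to OR 1.5 with 19 predictors raises it by roughly 10. At OR 1.5 the misses are 100 − 48 = 52%, 100 − 63 = 37% and 100 − 77 = 23%.

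**What a miss costs.** Large-sample calculation, all assumed except the plan's 25% and 1.72: log-odds slope of seeking on post-presentation intention 1 per SD; log-odds slope of dropout on it −0.7 (or −1.2 in the researcher-only arm). Youth anxiety is left out of this calculation.

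- Dropout 10% in each arm, equal slopes: bias about nil (true OR 1.29 stays 1.29).
- Dropout 12% researcher-only, 8% KOL: 1.28 becomes 1.26, log odds ratio about 8% too small.
- Dropout 15% researcher-only, 5% KOL, true OR 1.73: becomes 1.65 (slopes −0.7) or 1.59 (−1.2 in the researcher-only arm). Shortfall: 1 − ln 1.65/ln 1.73 = 1 − 0.501/0.548 = 9%; 1 − ln 1.59/ln 1.73 = 1 − 0.464/0.548 = 15%.
- Same split at a true OR of about 1.29: becomes 1.17-1.23, a larger share because the true effect is smaller.
- Split reversed at 1.29: about 1.34-1.36, so the bias can go either way.

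**Against sampling error.** With 81 per arm at 25% and 36.4%, the cells are 20.25, 60.75, 29.5 and 51.5. SE(log OR) = √(1/20.25 + 1/60.75 + 1/29.5 + 1/51.5) = 0.35. The 15%/5% shift at OR 1.73 is 0.05-0.08 on the log scale, or 0.14-0.24 SE.

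**The case against.** The strongest reply is that the harm is small and uncertain. Four parts of it stand.

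- The errors are asymmetric. A false alarm leads to imputation, which is the recommended method and adds little variance at 10% missing. High firing rates with no association are therefore no harm to the estimate.
- A reader might infer that the trigger is generally no better than chance. The numbers do not support that. With five predictors and a strong one (OR 2.0) it fires in 80% of trials against 22-24% with no association. The weakness is confined to weak and moderate predictors and long lists.
- A reader might also infer that complete cases are the default result. The plan does not say so. On these assumptions a list of 12 or more predictors triggers imputation in about half of trials or more. Complete cases are the likelier result only with a short list and no more than a moderate association.
- The bias depends on a dropout split that the plan does not predict. It expects 10% overall, citing a brief questionnaire. The detection odds ratios refer to baseline predictors and the bias slopes to post-presentation intention, so the probability of a miss together with material bias has not been quantified.

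Two further replies carry less weight. First, the rule speaks of differential association, which could be read as a comparison between arms; but condition is not in the stated predictor list. Second, no method can see missing outcomes, and imputation also assumes missing at random. That is true, but imputation conditions on post-presentation intention and complete-case regression does not.

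**Conclusion.** The concern holds in a limited form. The plan states a rule that can leave a primary outcome on complete cases because a weak check found nothing, while relevant post-presentation data are on file. The check leaves out condition and post-presentation intention, detects a moderate baseline predictor only about 36% of the time, and fires at a rate set largely by how many predictors are entered.

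The likely bias is nil to modest: about nil with equal dropout and slopes, and about 9-15% of the log odds ratio at the plan's effect size under an assumed 15% versus 5% split. That is well inside one standard error. Nothing in the documents shows that dropout will differ by arm, although participants are not blinded and the plan would not check.

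This rests on p < 0.05 as the trigger, 18 dropouts as a planning figure, independent predictors, 1:1 allocation, and complete-case analysis as an inference from the absence of any other named method. It is a worthwhile change to the SAP, not a threat to the trial's validity.

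**What to change.** Remove the trigger and specify the following:

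- Three-month CBT seeking is multiply imputed in all cases. The imputation model contains condition, school, pre- and post-presentation intention, youth anxiety and the baseline secondary measures.
- The complete-case logistic regression is reported as a sensitivity analysis.
- The retention regression is kept as description only, with condition added to its predictors.
- The pre/post multilevel models are fitted by likelihood to all available observations.

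The cost is a few sentences of SAP text and a little more analysis. The imputed result relies on a missing-at-random assumption, which should be stated. At the SAP date no three-month data had been collected and nothing had been analysed, so the rule could have been fixed then without any choice driven by the data. If it is changed now, the date of the change relative to data access should be recorded.

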#### Planned Analyses

**Quantitative Analyses:** All analyses will use multilevel modeling to account for the nesting of repeated measures within caregivers. Preliminary analyses will examine the effect of clustering of caregivers within schools. If schools account for more than 10% of variance in the outcomes after controlling for condition, a three-level multilevel model will be used to account for nesting of repeated measures within caregivers within schools.

Analyses will consider intention to seek CBT with exposures (Treatment Seeking Evaluation - Intention to seek CBT), subjective norms about seeking CBT (Therapy Subjective Norms Questionnaire—CBT), attitudes about CBT (Caregiver Attitudes about CBT), caregiver stigma about mental illness (Parents' Internalized Stigma of Mental Illness Scale), and knowledge about how to seek EBPs for youth anxiety (Parent Engagement in Evidence-Based Services Questionnaire—Knowledge Subscale) as person-level dependent factors; condition (caregiver or

researcher co-facilitator) as a person-level predictor; and time (pre- and post-presentation) as an observation-level predictor. In separate multilevel models, (a) intention to seek CBT, (b) Therapy Subjective Norms Questionnaire—CBT, (c) Caregiver Attitudes about CBT, (d) Parents' Internalized Stigma of Mental Illness Scale, and (e) Parent Engagement in Evidence-Based Services Questionnaire-Knowledge subscale will be regressed on time, condition, and the interaction between time and condition; a random intercept will be included in all five multilevel models. A binary logistic regression will be conducted with CBT service seeking at the threemonth follow-up (Treatment Seeking Evaluation - Actual CBT seeking) entered as the dependent variable, condition entered as the independent variable, and youth anxiety (Brief Revised Child Anxiety and Depression Scale-Total Anxiety) entered as a control variable. Ttests will be used to compare difference between conditions for each item on the Relatability Evaluation of the principal investigator. This study will examine caregiver demographic factors, youth anxiety (Brief Revised Child Anxiety and Depression Scale-Total Anxiety), racial similarity to the presenter (Demographics, same race), and self-disclosure (Content Checklist, selfdisclosure), as potential moderators of the effect of presentation condition on intention to seek CBT. In separate multilevel models, intention to seek CBT will be regressed on time, condition, each potential moderators, and their three-way interaction.

**Qualitative Analyses:** The transcribed qualitative interviews will be entered into NVivo software for analysis. Qualitative analyses will use a direct content analysis approach (Hsieh & Shannon, 2016). The coding team will create an initial codebook using the primary topics asked in the qualitative interviews. Additional codes will be added to code text that does not fit into the initial categories, either to split the initial codes into two, or to create new codes. Coding will occur through a consensus process in which each transcript will be coded independently by two raters, who will arrive at consensus through discussion (Hill et al., 2005). Thematic responses will be examined by both condition and by whether the caregiver has sought treatment for their youth (4 groups total).

**Integration Procedures:** Mixed methods integration will follow a QUAN → qual structure with an expansion approach (Palinkas et al., 2010); quantitative methods being used to test hypotheses about the intervention and qualitative methods being used to contextual the results.

**Data collection at the time of the SAP:** As of 8/11/21, pre/post presentation data has been collected from 17 participants. Three-month follow-up data has not yet been collected. No data has been analyzed.

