## **Primary Aims**

**Aim 1:** Test the relative effects of researcher-only and KOL conditions on changing caregivers' intention to seek CBT for their youth, and actual CBT seeking at three-month follow up.

*Hypothesis 1a:* Relative to the researcher-only condition, the KOL condition will result in a greater increase in intention to seek CBT with exposures.

*Hypothesis 1b:* Relative to the researcher-only condition, the KOL condition will result in a greater seeking of CBT with exposures for their youth at the three-month follow-up.

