## **MEASURES**

#### Primary outcome measure:

1. Change From Pre-Presentation to Post-Presentation in Treatment Seeking Evaluation - Intention to Seek Cognitive Behavioral Therapy [Time Frame: pre-presentation; post-presentation (within 1 week after the presentation)]

Participants rate how likely they are to seek a therapist who uses exposure therapy for their child in the next three months on a scale ranging from 1 (*very unlikely*) to 5 (*very likely*).

2. Number of Participants Who Sought Cognitive Behavioral Therapy as Assessed by Treatment Seeking Evaluation - Actual Cognitive Behavioral Therapy Seeking [Time Frame: 3-month follow-up]

Participants indicate whether they sought exposure therapy for their child since the presentation (yes/no).

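### The five pre/post models test the difference in mean change without using the baseline score for precision; a constrained-baseline model with a school level would be a cheap improvement

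*Combined protocol and SAP*

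**What the plan says.** Primary outcome 1 is defined as "Change From Pre-Presentation to Post-Presentation in Treatment Seeking Evaluation - Intention to Seek Cognitive Behavioral Therapy", and Hypothesis 1a predicts that "the KOL condition will result in a greater increase in intention to seek CBT with exposures". Under Planned Analyses, intention and four secondary scales (subjective norms, attitudes, stigma, knowledge) are each modelled separately. Each "will be regressed on time, condition, and the interaction between time and condition"; "a random intercept will be included in all five multilevel models". The plan enters "time (pre- and post-presentation) as an observation-level predictor", so there are two measurements per caregiver.

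Youth anxiety is measured before the presentation. In the logistic model for CBT seeking it is "entered as a control variable". For intention it enters only the moderator models, in which "intention to seek CBT will be regressed on time, condition, each potential moderators, and their three-way interaction".

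A school level is added only if schools explain more than 10% of outcome variance after controlling for condition.

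**The concern.** With two time points, complete data and a random intercept, the time by condition term equals the difference between arms in mean change. The condition main effect leaves the baseline means free to differ. The pre-presentation score is thus subtracted with a coefficient of 1, whatever its correlation with the post score. When the correlation is below 1, a smaller coefficient gives a smaller variance. Because schools are randomized, the arms have equal baseline means in expectation, and the model could use that.

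Two things are at stake. First, intervals for the primary intention outcome and the four secondary scales are wider than the collected data require. Second, the estimate moves with any chance baseline difference between arms, and such differences are more likely when whole schools are allocated than when individual caregivers are.

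**Working it through.** **Inputs from the documents.** N = 180, two-sided 5%, power .83 for a group effect of r = .30 on change, against r = .15 in the control group (Sample size). Two time points and the fixed effects as quoted (Planned Analyses). Allocation is by school (Randomization).

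**Inputs not in the documents, assumed.** Pre-post correlation rho; ICC; 18 caregivers per school (10 schools); equal arms of 90; equal pre and post variance, set to 1.

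**1. The plan's own .83.** It cannot be reproduced, because rho and the Monte Carlo model parameters are not given. At N = 180:
- a single correlation of .30 gives .98;
- a test of two independent correlations, .30 against .15, gives .18;
- converting each r to d = 2r/sqrt(1 - r²) gives .629 and .303, a difference of .326. As a difference in change, this has power .45, .59, .81, .87 and .93 at rho .3, .5, .7, .75 and .8.

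Only the last variant can match .83, at rho between .70 and .75. Below, .83 is taken as the power of the change contrast and used as a yardstick.

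**2. Precision, negligible clustering.** Per caregiver, the change variance is 2(1 - rho) and the baseline-adjusted variance is 1 - rho². The ratio is (1 + rho)/2. Power is rescaled as Phi[(0.954 + 1.960)/sqrt(ratio) - 1.960].

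| rho | variance ratio | SE reduction | power from .83 |
|---|---|---|---|
| .3 | .65 | 19% | .95 |
| .5 | .75 | 13% | .92 |
| .7 | .85 | 8% | .89 |

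**3. Precision with a school level.** Take m = 18, overall rho = .5 and school effects that do not change over time. A school mean has variance V = ICC + (1 - ICC)/m and pre-post covariance C = ICC + (rho - ICC)/m. The best coefficient for the baseline is C/V, and the variance ratio is (1 + C/V)/2.

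| ICC | V | C | C/V | variance ratio | power from .83 |
|---|---|---|---|---|---|
| .02 | .0744 | .0467 | .63 | .81 | .90 |
| .05 | .1028 | .0750 | .73 | .86 | .88 |
| .10 | .1500 | .1222 | .81 | .91 | .86 |

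If .5 is instead read as the within-school correlation, C = ICC + .5(1 - ICC)/18 and the ratios are .82, .87 and .92.

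**4. Why the school level must stay in.** A simulation of 6,000 trials per scenario (10 schools of 18, within-school rho .5, true effect 0.30 SD) compared the change contrast with an individual-level regression of post on pre with no school term. Empirical SDs were .148 against .136 at ICC .02, .145 against .144 at .05, and .142 against .154 at .10. Without a school term, the gain is gone near ICC .05 and reversed at .10.

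**5. Average bias and conditional shift.** In the same simulation at ICC 0, the change contrast averaged .299 to .301 against a true .30, so it is unbiased. Given a baseline difference, it shifted by -.69, -.50 and -.29 per unit at rho .3, .5 and .7, which is -(1 - rho) within simulation error; the adjusted estimate shifted by about 0. At rho .5, a 0.2 SD imbalance therefore moves the change estimate by .5 x 0.2 = 0.10 SD. Stable school effects weaken the shift: at within-school rho .5 it was -.37, -.26 and -.17 per unit at ICC .02, .05 and .10.

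**6. If the baseline difference is systematic.** With a stable arm difference of 0.2 or 0.3 SD at rho .5 and no school effect, the change contrast averaged .302 or .301, and the adjusted estimate .401 or .451 (true value .30). This agrees with .30 + (1 - .5) x 0.2 = .40 and .30 + (1 - .5) x 0.3 = .45. A model that constrains baseline means to be equal rests on the same assumption.

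**The case against.** The strongest defence is that the plan does what it says. Hypothesis 1a is about a greater increase, the outcome is a change, and the time by condition term tests exactly that. This stands.

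A reader might infer that the planned estimate suffers regression-to-the-mean bias. The documents do not support that. Allocation is random by school, so the change contrast is unbiased over randomizations; what remains is a shift given chance imbalance, which can favour either arm. The 1 to 5 response scale does not rescue the inference, since a linear baseline-adjusted model meets the same ceiling.

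A reader might also infer that adjustment is free. It is not. The Study Design section says that neither researchers nor participants are blinded, KOLs are picked for their standing among local caregivers, and the timing of enrolment relative to allocation is not given. If attendance depended on condition, the change contrast is robust to a stable arm difference and the constrained model is not (step 6). This is the main reservation.

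Nor is it an inconsistency that the seeking model has "and youth anxiety (Brief Revised Child Anxiety and Depression Scale-Total Anxiety) entered as a control variable" while the intention model does not. The seeking outcome has no pre-presentation score, and adding youth anxiety only as a main effect to the planned model would leave the change contrast as it is.

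Finally, the larger gains belong to low rho and negligible clustering. If rho is .70 to .75, as the one variant that can match .83 would require, the SE reduction without clustering is only 8% to 6% (1 - sqrt(.85) = .078; 1 - sqrt(.875) = .065). That limits the size of the point, not its direction.

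**Conclusion.** The point holds as an efficiency improvement, not as an error. The planned models are valid for Hypothesis 1a but leave out information that the trial collects. Across the assumed values, the variance of the main contrast could fall to between .65 and .91 of its planned size. With clustering at ICC .02 to .10, the more realistic part of that range is .81 to .91, equivalent to raising a power of .83 to between .90 and .86.

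These figures rest on an assumed rho, ICC and school size, on school effects that are stable over time, on known variances and on a normal approximation. They also take the stated .83 as the power of the change contrast, which the documents do not allow one to confirm. The gain survives clustering only if the school level is in the model, and the constraint is safe only if caregivers did not select into attendance by condition.

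**What to change.** For the five pre/post outcomes, prespecify as the main analysis the mixed model with baseline means constrained equal across conditions: keep time and time by condition, and drop the condition main effect. The tested term and the wording of Hypothesis 1a stay the same. Keep the school level in this model whatever the 10% rule would decide; an ICC of .05 would fall below that threshold, yet leaving schools out would remove almost all of the gain (step 4). Report the unconstrained change contrast alongside as a sensitivity analysis.

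State when caregivers enrolled relative to allocation and whether they knew their school's condition. If enrolment followed known allocation, give the two analyses equal prominence.

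The cost is SAP wording plus the small risk of bias described above. At the SAP date, 17 participants had pre/post data and nothing had been analyzed, so the change could be made before any results were seen. If analysis has since begun, label the constrained model as post hoc.

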#### **INTERVENTIONS**

**Presentation:** The outreach presentation will last 75 minutes with an additional 15 minutes for caregiver questions. The presentations will occur in the evening via Zoom. The presentation will include information about identifying anxiety disorders, strategies for caregivers to help their youth with anxiety, evidence-based practices to treat youth anxiety, and strategies for finding a therapist who uses cognitive behavior therapy with exposures. The text on the presentations is written at a 5.3 grade reading level. Presentations will incorporate stigma reduction strategies, such as education to dispel myths, and behavioral decision-making tools to elicit hope, empowerment, and motivation.

**Researcher-Only condition:** The researcher-facilitated presentation, led by two clinical psychology graduate students, will be the same for all schools.

**Key opinion leader:** The key opinion leader (KOL) co-facilitated presentations will include the same core principles as the researcher-facilitated presentation but may vary by school in terms of specific examples and content emphasized based on KOL feedback. A caregiver KOL from the local community will co-facilitate the presentation with a clinical psychology graduate researcher. To select the KOLs, the principal investigator will contact the school PTA (or a similar parent group), and PTAs will be asked, "please nominate a caregiver who is well-known and respected within your community, and who reflects the diversity of the school as a whole." The PI will meet with the KOLs to review the presentation and to engage them in championing cognitive behavior therapy for youth anxiety.

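### The five pre-post models carry only a random intercept, so the time-by-condition test ignores within-school correlation of change in a school-randomized trial

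*Combined protocol and SAP*

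**What the plan says.** The Randomization paragraph allocates whole schools: "Participants will be cluster randomized by school using restricted randomization".

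Under Planned Analyses, the default model nests repeated measures within caregivers and has no school level. School enters conditionally: "If schools account for more than 10% of variance in the outcomes after controlling for condition", then "a three-level multilevel model will be used to account for nesting of repeated measures within caregivers within schools". Intention, subjective norms, attitudes, stigma and knowledge each "will be regressed on time, condition, and the interaction between time and condition". Condition is entered "as a person-level predictor; and time (pre- and post-presentation) as an observation-level predictor". The only random effect named is in the statement that "a random intercept will be included in all five multilevel models".

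The plan specifies no school-by-time random effect, cluster-robust variance, school-level test or small-sample degrees of freedom.

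Two other places bear on this. Under Interventions, KOL presentations "may vary by school in terms of specific examples and content emphasized based on KOL feedback", while researcher-only content is uniform. The Sample size paragraph reports that for 180 participants and a two-sided 5% test, "statistical power was .83 to detect a medium-sized effect", without giving a number of schools or an ICC.

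**The concern.** Hypothesis 1a is about the increase in intention, so it is tested by time-by-condition. The error that matters for that term is how much the average change varies between schools of the same arm. A random intercept describes school differences in level, which a pre-post contrast removes anyway. It says nothing about school differences in change.

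Such differences are plausible. Each KOL is nominated through a school's parent group and the content may be adapted to the school. The Content Checklist also records self-disclosure by a presenter or audience member, and the plan tests this as a moderator of the effect on intention. The plan therefore allows that something shared by an audience may affect change.

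The primary intention test and the four secondary pre-post tests are affected. For Hypotheses 1a and 2a, a standard error that is too small produces false differences between arms. For Hypothesis 2b, which predicts a similar increase in knowledge, it works against the hypothesis. The three-month logistic regression is a separate matter and is not covered here.

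**Working it through.** **1. The plan's own figure.** The .83 cannot be reproduced from the stated inputs. With 90 per arm (assumed) and d = 2r/√(1−r²), r = .30 gives d = .629 and power .99; r = .15 gives d = .303 and power .53; the difference, .326, gives .59 (all two-sided). Of the readings tried, .83 appears only if a pre-post correlation of about .72 is assumed and change scores are tested: change SD √(2(1−.72)) = .748, .326/.748 = .435, power .831. The documents give no such correlation, so .83 is neither confirmed nor refuted. It serves below only as an anchor for the power cost.

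**2. Why the intercept cancels.** Write the score of caregiver i in school j at time t (0 or 1) as fixed effects + u_j + v_ij + b_j·t + e_ijt, where u is the school intercept, v the caregiver intercept and b the school deviation in change. Post minus pre is:

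D_ij = β_time + β_interaction·condition_j + b_j + (e_ij1 − e_ij0)

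Both u_j and v_ij have gone. With n caregivers per arm, m per school, change variance σ² and change ICC ρ = var(b)/σ²:

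- variance used by the stated model: 2σ²/n
- true variance, both arms varying: (2σ²/n)·[1 + (m−1)ρ]

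The school variance is not lost. It goes into the residual as if independent between caregivers. What the standard error lacks is the factor √[1 + (m−1)ρ].

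**3. Check by fitting the models.** In 60 REML fits (10 schools of 18, level ICC .12, change ICC .05, pre-post correlation about .6), the time-by-condition standard errors of the two-level and the three-level random-intercept models equalled the unclustered change-score value to within 0.000003 in every fit (mean .131). Adding a school random slope for time gave a mean of .180. The true value is √(.8 × (2/90) × 1.85) = .181. In separate fits with 15% of post scores missing, adding the school intercept moved the standard error by no more than 0.0002.

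**4. Type I error of the stated test.** Assumptions: 180 caregivers, equal schools, half per arm, 40,000 simulated trials per cell, nominal 5%.

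| Schools | Arms varying | ICC 0 | .01 | .02 | .05 | .10 |
|---|---|---|---|---|---|---|
| 6 | both | 5.1% | 8.4% | 12.1% | 21.7% | 33.0% |
| 10 | both | 5.0% | 7.1% | 8.8% | 15.4% | 23.7% |
| 18 | both | 5.1% | 6.1% | 6.9% | 10.3% | 15.4% |
| 30 | both | 4.9% | 5.7% | 5.9% | 8.3% | 11.0% |
| 6 | KOL only | 4.8% | 6.7% | 8.5% | 13.6% | 22.0% |
| 10 | KOL only | 5.1% | 6.0% | 7.0% | 10.3% | 15.5% |
| 18 | KOL only | 5.0% | 5.5% | 6.2% | 7.8% | 10.5% |
| 30 | KOL only | 4.9% | 5.4% | 5.4% | 6.6% | 8.2% |

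Hand check for 10 schools, ICC .05, both arms: 1 + 17 × .05 = 1.85; 1.973/√1.85 = 1.451; two-sided tail 14.7%, against 15.4% simulated.

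**5. The remedies under the null.** A t-test on school mean changes stayed at 4.7–5.2% with both arms varying and 4.8–6.3% with only the KOL arm varying; the Welch version stayed at 3.3–5.1%. The random-slope model with school-based degrees of freedom never exceeded 5%, and was conservative with few schools (about 0.4–4% at 6 schools).

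**The case against.** **The triggered model is under-described, not wrong.** The three-level model gets one sentence, and a school slope is not excluded in so many words. The Measures section also defines these outcomes as change from pre to post, so the 10% rule might be read as applying to variance in change. This stands as a point about certainty, but it does not rescue the plan. The SAP names an intercept for all five models and a slope for none. Even on the change reading, the two-level model is kept below 10%, and at a change ICC of .05 with 10 schools that means about 15% false positives with both arms varying.

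**The size is unknown.** This is true. With 30 schools and a change ICC of .01 to .02, the error is about 6%, or about 5% if only the KOL arm varies. At ICC 0 the planned test is correct.

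**The named source of variation lies in the KOL arm.** If KOLs made no difference at any school, KOL-specific variation would be zero, and the KOL-only rows describe a zero average effect that differs by school. This is fair, and those rows are the ones to read for that mechanism. Audience self-disclosure, however, can occur in either arm.

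**Restricted randomization may reduce the inflation.** The simulations used unrestricted allocation. If the restriction factors, which the plan does not name, predict change, the inflation is smaller and schools-minus-2 degrees of freedom may need adjusting. This also stands.

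**The person-level label for condition is weak evidence.** Agreed: the person is the top level of the default model. The point rests on the random effects, not on the label.

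**Conclusion.** The concern holds. As written, the five pre-post tests treat caregivers as independent with respect to change although schools were randomized, and the 10% rule does not alter this on either side of the threshold. The cancellation is exact for complete pairs and near enough with 15% of post scores missing.

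If schools do not differ in change, the tests keep their 5%. If they do, type I error exceeds 5%, and the stated models would not reveal it. The range of 5% to 33% rests on assumed school numbers (6 to 30), assumed change ICCs (0 to .10), equal school sizes and unrestricted allocation. This is an analysis rule that gives the wrong error for the randomized unit, not merely a missing detail, and it should be corrected before analysis.

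**What to change.** In all five models, whatever the observed ICC, include a school-by-time random effect (a school random slope for time) alongside the caregiver and school intercepts. Test time-by-condition with small-sample degrees of freedom based on the number of schools, adjusted for restriction factors if these are modelled. Drop the 10% rule for these models. If the model does not converge, compare school mean changes between arms, using the Welch version if only the KOL arm may vary. State the number of schools. Regressing the post score on the pre score with a school random intercept is also valid, but it is a different estimator and should be named as such if chosen.

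This needs SAP wording and one variance component, with no extra participants. As of the date in the SAP, 17 participants had pre/post data and nothing had been analyzed, so the wording could be set without sight of results.

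It is not free. Intervals widen, and slope models may fail to converge or be conservative with few schools. Even if the slope variance is estimated at zero, the critical value rises from about 1.97. Taking .83 as power without school variation in change (d = .437 in change-SD units), and using a noncentral t with schools-minus-2 degrees of freedom and the design effect above with both arms varying:

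| Schools | Critical value | Power, ICC 0 | ICC .02 | ICC .05 |
|---|---|---|---|---|
| 6 | 2.78 | .60 | .43 | .30 |
| 10 | 2.31 | .73 | .60 | .47 |
| 18 | 2.12 | .79 | .72 | .63 |
| 30 | 2.05 | .81 | .77 | .72 |

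These powers are illustrative, because the .83 itself could not be confirmed.
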